### **7.2 Exclusion Criteria**

1. Severe renal dysfunction (eGFR < 30 ml/min/1.73m^2)
2. Requirement for inotropes (other than digoxin) or mechanical support during hospitalization
3. Clinically significant electrical instability during hospitalization
4. Ongoing need for other intravenous therapies beyond diuretics (vasodilators, antibiotics, etc.)
5. Anticipated need for ongoing parenteral electrolyte repletion
6. Planned discharge to location other than home (e.g, hospice, skilled nursing facility, etc.)
7. Anticipated cardiac transplantation or left ventricular assist device within the next 30 days
8. Primary hypertrophic cardiomyopathy, infiltrative cardiomyopathy, acute myocarditis, constrictive pericarditis or tamponade
9. Known or anticipated pregnancy in the next 30 days
10. Prior use of subcutaneous furosemide pump or current use of any subcutaneous pump, on-body infusion devices or patients who give regimented injections at the intended site of the furosemide infusion device
11. Other psychosocial or physical barriers to following the protocol and using a subcutaneous pump device outside the hospital setting
12. Unable to accurately measure urine output
13. Known allergy to furosemide
14. Known sensitivity or allergy to medical adhesive tape

## **8.0 TREATMENT INTERVENTIONS**

### ***8.1 Inpatient Pilot***

Eligible patients who are in the hospital for AHF will receive subcutaneous furosemide, with planned treatment for 48 hours. Subject's last dose must start prior to 48-hour time period and will have a maximum of 4 doses. They will be treated with 5-hour 80 mg subcutaneous furosemide injection either once or twice daily, based on clinical assessment of diuretic requirements. Assessment of renal function and electrolytes will be performed as clinically indicated consistent with standard of care for inpatient treatment of AHF. The subjects will be instructed on the pump and have it applied for the first dose. The subjects will be encouraged to apply the pump while supervised at their next dosing. Subjects will be phoned at day 9 to collect safety data.

### ***8.2 Outpatient Pilot***

Eligible patients who are in the hospital for AHF will receive subcutaneous furosemide at hospital discharge, with planned treatment for 1-7 days in the outpatient setting. They will be treated with 80 mg subcutaneous furosemide injection over 5 hours either once or twice daily, based on clinical assessment of diuretic requirements. Prior to discharge the subjects will be instructed on the pump and the subject will apply it, while supervised. It is anticipated that the subject will then be discharged and they will self-administer pump at home for remainder of usage. In subjects whose hospitalization extends beyond the anticipated period, the protocol driven assessments should occur during the inpatient stay when possible.

#### **8.2.1 Subcutaneous furosemide outpatient strategy:**

Subjects will receive device training and study materials (subcutaneous pump device and 7-day supply of subcutaneous furosemide vials) on the day of planned hospital discharge (study day 0). It is assumed the subject will be discharged within 24 hours. If they are not discharged within 24 hours the subject will remain on the pump as ordered by the treating physician. Training will include instruction on daily weights and dyspnea numerical rating for symptoms. Scales will be provided to all subjects. Subjects will be discharged with a planned treatment with 80 mg 5-hour subcutaneous furosemide injection either QD or BID depending on anticipated diuretic requirements. If there are unanticipated delays in discharge after enrollment, subjects will continue with their assigned therapy and assessments in the hospital. Discharged subjects will receive a phone contact from study team on D1, D3, and D5 in order to assess adequacy of diuresis, persistence of congestion, and planned duration and dose of ongoing subcutaneous therapy (see Appendix C for guidelines on adjusting therapy). Additional clinical contact (additional phone contacts or clinical visits) may be performed if felt clinically indicated by the study team or clinical provider. All subjects will have a clinic visit at Day 7 (+2) and a safety follow up phone call at Day 14. Subjects will have assessment of electrolytes and renal function by protocol at 48 hours from discharge. Day 2 (+2) labs can be done at the study site or via home laboratory testing that is set up by study site prior to discharge if assurances are made that results will be sent to the study team in a timely manner (<24 hours). More frequent electrolyte monitoring can be performed at the discretion of the study team or clinical provider as clinically indicated. Subjects receiving the subcutaneous pump for outpatient use should be

prescribed a supplementation regimen based on electrolyte supplementation needs in the hospital with IV therapy. The duration of subcutaneous therapy will be planned from 1-7 days depending on clinical response. Dose and frequency of oral diuretics once subcutaneous therapy is completed will be per the discretion of the treating physician.

### ***8.3 Diuretic Dose Adjustments***

Diuretic therapy will be adjusted as needed based on clinical assessment of signs and symptoms of congestion, vital signs, laboratory values, and diuretic response by their attending provider. All study participants will be on 80mg subcutaneous by subcutaneous pump either once or twice daily. Outpatient pilot subjects will be prescribed either 80mg subcutaneous by subcutaneous pump either once or twice daily at hospital discharge depending on the provider assessment of their degree of congestion and diuretic responsiveness. For inadequate diuretic response, providers may either increase to 80mg subcutaneous BID (if initially treated with 80mg subcutaneous QD) or add additional open label oral diuretics, or other adjunctive treatments (such as metolazone, based on clinical judgment). The timing and dosage of the decision to discontinue subcutaneous therapy and switch to oral diuretics will be based on clinical judgment. Outpatients may not continue subcutaneous therapy beyond day 7. If subjects are readmitted for heart failure during the treatment period, subcutaneous therapy should be discontinued and the patient treated with IV diuretics as clinically indicated.

### ***8.4 Electrolyte Repletion***

Repletion of electrolytes will be based on clinical assessment of potassium and/or magnesium balance and subject's prior need for supplementation. The extent of ongoing electrolyte monitoring will be based on clinical judgment.

### ***8.5 Concomitant Medications***

Other than SUBQ pump diuretic therapy, all subjects will be treated with standard of care heart failure therapy as directed by treating providers. Information on cardiovascular medications, diuretics and electrolytes will be collected.

## **9.0 RECRUITMENT PROCEDURES**

All patients admitted to the participating Heart Failure Clinical Research Network centers with a diagnosis of AHF will be screened for possible participation in the study. Given that the protocol requires patients to be stabilized for at least 18 hours of IV therapy prior to enrollment, this will allow for identifying and following potential patients for eligibility. Patients meeting eligibility criteria will be approached regarding participation in this study. Patients who agree to participate will be enrolled. There is no screening period in this study.

## 10.0 STUDY SCHEDULE

A complete schedule of assessments throughout the pilot study is provided in **Appendix A**.

### ***10.1 Baseline Evaluation: Inpatient Pilot***

At the time of enrollment, all study subjects will undergo:

- Directed history and physical examination, focused on signs and symptoms of congestion
  - Vital signs (including weight)
  - NYHA Classification prior to decompensation
  - Input and Output measurement starts at enrollment (time of consent)
  - Review of concomitant cardiovascular medications, diuretics and electrolyte supplementation
  - Baseline NTpro-BNP or BNP, creatinine, BUN, and electrolytes (local laboratory), pregnancy test (if female and if not done during hospitalization)
  - Numerical rating score (0-10 point NRS) for symptoms (see **Appendix B**)
- Assessments and labs done as usual care within 4 hours of enrollment may be collected and entered into the eCRF for the study.

Once the baseline data points have been collected, a member of the study team will teach the subject about the subcutaneous pump and the infusion will be started.

#### **10.1.1 Study Days 1-2**

For study days 1-2 the following will be collected daily:

- Physical examination focused on signs and symptoms of congestion
- Daily AM weight post void
- Numerical rating score (0-10 point NRS) for symptoms
- Total inputs and outputs (i.e. fluid balance)
- Daily furosemide dose plus any rescue therapy (i.e. need for additional diuretics)
- Need for electrolyte supplementation and dose
- Lab values for basic metabolic panel (only if done per standard of care)
- Assessment for adverse events

#### **10.1.2 Study Day 9**

There will be a phone visit for all subjects 9 days (+2 days to allow for arranging the call on a weekday) post enrollment.

Assessments during this phone call will include:

- Assessment for adverse events
- Assessment for interval hospitalizations, ED visits, or unscheduled clinic visits

## **10.2 Baseline Evaluation: Outpatient Pilot**

At the time of enrollment, all study subjects will undergo:

- Directed history and physical examination, focused on signs and symptoms of congestion
- Vital signs (including weight)
- NYHA Classification prior to decompensation
- Concomitant cardiovascular medications, diuretics and electrolyte supplementation
- Baseline creatinine, BUN, NT-proBNP or BNP, and electrolytes (local laboratory, standard of care), pregnancy test (if female of child bearing potential and not done during hospitalization)
- Numerical rating score (0-10 point NRS) for symptoms (see **Appendix B**)
- Assessment for adverse events

Assessments and labs done as usual care within 12 hours prior to enrollment may be collected and entered into the eCRF for the study.

Once the baseline data points have been collected, and prior to discharge, a member of the study team will teach the subject on the use of the subcutaneous pump and the subject will apply it for their first dose while supervised.

### **10.2.1 Study Days 1 through 7**

For study days 1-7, the following will be collected daily. These data will be recorded daily by the subject and reported to the study site during phone contacts:

- Daily AM weight (from chart if subject in hospital, self weigh if home). Subjects will be instructed to collect an AM post-void weight and record this information.
- Numerical rating score (0-10 point NRS) for symptoms (subject recorded)
- Total diuretic dose
- Electrolyte supplementation (type and dose)
- Assessment for adverse events
- Assessment for interval hospitalizations, ED visits, or unscheduled clinic visits

### **10.2.2 D1, D3 & D5 Phone Call**

There will be a phone visit for all subjects 1, 3, and 5 days post enrollment.

Assessments during each phone call will include:

- Weight (patient reported)
- Numerical rating score (0-10 point NRS) for symptoms (patient reported)
- Changes in diuretic dose
- Electrolyte supplementation
- Assessment for adverse events
- Assessment for interval hospitalizations, ED visits, or unscheduled clinic visits
- Any problems with the pump use or drug

### **10.2.3 D2 Lab Visit**

On study day 2 (window: + 2 days), subjects will undergo laboratory testing of BUN, creatinine, and electrolytes. Labs can be done at the study site or via home laboratory testing that is set up by study site prior to discharge if assurances are made that results will be sent to the study team in a timely manner (<24 hours).

### **10.2.4 D7 Clinic Visit**

There will be a protocol specified clinic visit for all subjects who have been discharged. This will occur on day 7 (+ 2 days to allow for arranging clinic visit on a weekday) post enrollment. Out-patient subjects may not continue subcutaneous therapy beyond day 7.

Assessments will include:

- Directed history and physical examination, focused on signs and symptoms of congestion.
- Vital signs (including weight)
- Numerical rating score (0-10 point NRS) for symptoms
- Creatinine, BUN, and electrolytes
- Changes in cardiovascular medications
- Assessment for adverse events
- Assessment for interval hospitalizations, ED visits, or unscheduled clinic visits
- Blood sample for BNP or NT-proBNP (local)
- Total diuretic dose
- Electrolyte supplementation (type and dose)
- Any problems with the pump use or drug
- Return pump and all used and unused vials, cartridges and diary

### **10.2.5 D14 Phone Call**

There will be a phone visit for all subjects 14 days (+2 days to allow for arranging the call on a weekday) post enrollment.

Assessments during this phone call will include:

Assessment for adverse events

Assessment for interval hospitalizations, ED visits, or unscheduled clinic visits

## **11.0 PARTICIPANT SAFETY AND ADVERSE EVENTS**

### ***11.1 Definitions***

#### **11.1.1 Adverse Events**

An adverse event (AE) is any untoward medical occurrence associated with the use of a drug in a subject whether or not considered drug or biologic related. An AE can therefore be any unfavorable and unintended sign, symptom or disease temporally associated with the use of a pharmaceutical product or biologic.

### 11.1.2 Suspected Adverse Reaction

A suspected adverse reaction (SAR) is any adverse event for which there is a reasonable possibility that the drug caused the event. “Reasonable possibility” suggests there is a causal relationship between the drug and the adverse event. “Suspected adverse reaction” implies a lesser degree of certainty about causality than adverse reaction, which means any adverse event caused by a drug.

### 11.1.3 Serious Adverse Events

An AE or SAR is considered serious if the Investigator or sponsor believes any of the following outcomes may occur:

- Death
- Life-threatening AE: Places the subject at immediate risk of death at the time of the event as it occurred. It does not include an AE that, had it occurred in a more severe form, might have caused death.
- Persistent or significant incapacity or substantial disruption of the ability to conduct normal life functions.
- Inpatient hospitalization or prolongation of hospitalization.
- Congenital anomaly or birth defect.
- Important medical events that may not result in death, be life threatening, or require hospitalization may be considered a serious adverse event when, based upon appropriate medical judgment, they may jeopardize the subject and may require medical or surgical intervention to prevent one of the outcomes listed in this definition above.

This determination is based on the opinion of either the investigator or sponsor (e.g., if either believes it is serious, it must be considered serious).

### 11.1.4 Laboratory Test Abnormalities

For laboratory test abnormalities that meet the definition of a serious adverse event (SAE), which required the subject to have the investigational product discontinued or interrupted, or required the subject to receive specific corrective therapy, the clinical diagnosis rather than the laboratory term will be used by the reporting investigator (e.g., anemia versus low hemoglobin value).

### 11.1.5 Assessment of Severity

The determination of adverse event severity rests on medical judgment of a medically qualified investigator. The intensity of AEs will be graded using the following definitions:

**Mild:** awareness of sign, symptom, or event but easily tolerated.

**Moderate:** discomfort enough to cause interference with usual activity and may warrant intervention.

**Severe:** incapacitating with inability to do usual activities or significantly affects clinical status, and warrants intervention.

### 11.1.6 Assessment of Causal Relationship

A medically-qualified investigator must assess the relationship of any AE to the use of study drug, based on available information, using the following guidelines:

- **Not related:** There is not a reasonable causal relationship to the investigational product and the adverse event.
- **Unlikely related:** No temporal association or the cause of the event has been identified, or the drug or biologic cannot be implicated.
- **Possibly related:** There is reasonable evidence to suggest a causal relationship between the drug and adverse event.
- **Related:** There is evidence to suggest a causal relationship, and the influence of other factors is unlikely.

The Investigator reports causality, but the sponsor retains the final decision on causality when filing to the FDA.

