## 11.2 Suspected Unexpected Serious Adverse Reaction

AEs that meet the criteria of serious, related to study drug, and unexpected per investigator brochure, qualify for expedited reporting to the regulatory authorities. The sponsor or their designee will notify the FDA and all participating investigators in a written IND safety report of an SAR that is serious and is unexpected, as determined by the sponsor. The reporting will occur as soon as possible, but not later than 15 calendar days after sponsor determines that it qualifies for expedited reporting. The sponsor will identify all safety reports concerning a similar SAR, and will analyze the significance of the SAR in light of the previous, similar reports. Follow-up reports will be sent to investigators to inform and update them about an important suspected adverse reaction if it significantly affects the care of the participants or conduct of the study.

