## 11.6.3 Device Adverse Reactions

### SC2Wear System

Mild skin irritation such as redness, itching and edema or skin trauma and abrasion may occur during exposure or removal of the adhesive. Removal of the device may be uncomfortable or painful. Rarely, allergic reactions to the adhesive may occur. If the subject knows they are sensitive or allergic to medical adhesive tape, they should not participate in the study.

The needle used to inject the drug into the subcutaneous tissue is automatically inserted at the beginning of the infusion cycle, and automatically retracted at the end. The needle is 27 gauge and 8.5 mm. Common risks with needle injection include pain or discomfort upon needle injection, or minor bruising from needle movement. Injection site reactions were minimal and limited to very slight edema and very slight to definite erythema. An accidental needle stick injury may occur if (a) the needle appears before the Pump is placed on the body or (b) the Pump falls off the body while it is pumping. If either of the above happens, the Pump should be handled carefully.

As with all devices that use medical adhesives for adherence the usual risks are: it is possible that there may be instances of complete or near complete dislodgement of the device from the abdominal skin. In a previous study designed to look at adhesive effectiveness in combination with the sc2Wear device, 2 out of 132 device applications (1.5%) became completely detached from the skin. In the same study 6 subjects (4.5%) had evidence of medical adhesive-related skin injury (MARSI). The finding of rare cases of dislodgement and rare cases of MARSI indicate that the objective to find an adhesive with the optimal balance between adhesive strength and skin tolerability has been achieved. Using more aggressive adhesive would increase the risk of MARSI which carries a risk of infection and may reduce the patient acceptance of this treatment. Should dislodgement occur, there would be minimal risk to the patient, as it would be obvious and clearly discoverable by the patient being treated. In such instances, the patients will be instructed to call their healthcare provider. In this study, patients are instructed to contact the study team in case of complete dislodgement or if leakage is detected.

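### Causality rating and expedited reporting refer to the study drug only, so harms caused by the pump, needle or adhesive have no clear attribution and no route to expedited notice

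*Combined protocol and SAP*

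**What the plan says.** All references are to the combined protocol and SAP.

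- **What is tested.** Section 3.2 identifies the SC2Wear pump as the device under test. The only objective (4.1) is whether a strategy of this new delivery route is safe and feasible.
- **AE definition (11.1.1).** An AE is "any untoward medical occurrence associated with the use of a drug in a subject whether or not considered drug or biologic related".
- **Suspected adverse reaction (11.1.2).** This requires a reasonable possibility that the drug was the cause.
- **Causality (11.1.6).** The investigator "must assess the relationship of any AE to the use of study drug" on a four-level scale. The top level names no agent. The second from the top is tied to the drug by its wording: "There is reasonable evidence to suggest a causal relationship between the drug and adverse event". The level below that one, for events thought unlikely to be related, is defined as "No temporal association or the cause of the event has been identified, or the drug or biologic cannot be implicated". The bottom level is framed around the investigational product, a term the protocol does not define.
- **Expectedness (11.1.7).** Judged against the reference documents for the study drug.
- **Expedited reporting (11.2).** "AEs that meet the criteria of serious, related to study drug, and unexpected per investigator brochure, qualify for expedited reporting". The duty to notify the FDA and investigators then applies to suspected adverse reactions that are serious and unexpected.
- **Back-up SAE form (11.3).** It carries the investigator's view of causality to study drug.
- **Device harms (11.6.3).** Listed apart from drug reactions: adhesive skin injury, needle pain and bruising, accidental needle stick, and dislodgement. In an earlier adhesive study, "2 out of 132 device applications (1.5%) became completely detached from the skin", and 6 subjects (4.5%) had adhesive-related skin injury.

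**The concern.** The new component in this pilot is the delivery system; furosemide itself is established. The attribution chain nevertheless asks only about the drug, and the text has no device-relatedness question and no device route to expedited notice.

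Two things are at stake. First, the Steering Committee and DSMB use the pilot to decide whether the main study, of about 300 patients, goes ahead as designed (2.0 and the end of 5.2). They need to see which harms came from the pump. With a drug-only question, a pump-caused AE and an AE with no link to treatment can carry the same code. Second, a serious, unexpected harm caused purely by the device does not meet the stated condition for prompt notice to the FDA and the other investigators.

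**Working it through.** **Step 1: trace one event through the text.** Take a serious infected adhesive injury with no contribution from furosemide.

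- 11.1.1: it is an AE, because relatedness is not required.
- 11.1.6, possibly related: not available, since this category needs a link to the drug.
- 11.1.6, unlikely related: fits, because another cause is identified and the drug cannot be implicated.
- 11.1.6, not related: fits if *investigational product* means furosemide alone, but not if it includes the pump. The term is not defined.
- 11.1.6, related: names no agent, but sits under an opening question about study drug.
- 11.1.2: not a suspected adverse reaction, because the drug is not the suspected cause.
- 11.2: fails the relatedness condition, so the trigger is not met even if the event is serious and unexpected.
- 11.3: as a non-exempt SAE it still reaches the sponsor within 24 hours.

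So the event is recorded, its causality code depends on how a site reads an undefined term, and the expedited route does not open.

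**Step 2: trace a delivery failure.** Suppose a detached pump is followed by worsening HF that meets the 11.5 definition. Sections 11.3 and 11.5 take it out of AE/SAE capture and put it on a separate eCRF module, for which the plan asks no causality rating. A device question placed only on the AE form would miss it.

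**Step 3: reproduce the stated rates (11.6.3).**

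- Detachment: 2/132 = 1.5%, per application.
- Skin injury: 6/132 = 4.5%. The section counts subjects here, but the percentage reproduces only with the 132 applications as denominator; the number of subjects in that study is not given. I treat 6/132 as a per-subject rate, which is an assumption.

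**Step 4: scale in this pilot.** Each phase has 20 subjects (2.0).

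- Applications, low: inpatients once daily for 48 hours (2 each) and outpatients once daily for 1 day (1 each): 20 × 2 + 20 × 1 = 60.
- Applications, high: inpatients at the 4-dose maximum and outpatients twice daily for 7 days (14 each): 20 × 4 + 20 × 14 = 360.
- Expected detachments: 60 × 2/132 = 0.9 to 360 × 2/132 = 5.5. Chance of at least one: 1 − (1 − 2/132)^60 = 60%, to 1 − (1 − 2/132)^360 = 99.6%.
- Expected skin injuries: 40 × 6/132 = 1.8. Chance of at least one: 1 − (1 − 6/132)^40 = 84%. Per phase of 20: 0.9 expected, 61%.

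The rates rest on few events. Exact 95% intervals are 0.2% to 5.4% for 2/132 and 1.7% to 9.6% for 6/132, so these counts show order of magnitude only.

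**The case against.** The strongest reply is that little is lost. AEs are collected whatever their cause. Non-exempt SAEs go to the sponsor within 24 hours regardless of relatedness or expectedness (11.3). Outpatient calls and the day 7 visit record pump problems (10.2.2, 10.2.4), and subjects are told to report dislodgement or leakage (11.6.3). The sponsor keeps the final say on causality for FDA filing (11.1.6). Most device harms will be mild, and the analysis is descriptive. The investigator brochure and the eCRF are not in the documents and may already hold a device item.

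Most of this stands, and it confines the point to attribution and expedited notice. It does not close the gap. The sponsor's final decision still runs through 11.1.2 and 11.2, which are drug-only. Pump-problem entries carry no causality rating, and the inpatient visit lists (10.1.1, 10.1.2) have no such entry.

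Three stronger readings are tempting, and the documents do not support them:

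- A reader might infer that the plan classes device harms as not related. It never says so; unlikely related is equally open, and *investigational product* could be read to include the pump.
- A reader might infer that the safety tables would understate treatment-related harm. No table by relatedness is planned: 12.2 compares overall AE rates and severity with expected rates, and an adhesive injury recorded as an AE counts there whatever its rating.
- A reader might apply the skin-injury rate to every outpatient application at the 7-day maximum: 140 × 6/132 = 6.4 once daily, 280 × 6/132 = 12.7 twice daily. But 11.6.3 reports subjects, and treatment lasts 1 to 7 days. Nor does every detachment need a causality category, since one without harm is not an AE.

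**Conclusion.** The point holds as a gap in attribution and in the expedited trigger, not in the capture of events or in overall AE rates. It rests on the wording of 11.1.2, 11.1.6, 11.1.7, 11.2 and 11.3 and does not depend on the counts.

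The counts show that the question will probably arise: about 0.9 to 5.5 detachments over an assumed 60 to 360 applications, and about 1.8 skin injuries among 40 subjects on the per-subject assumption. They say nothing about how often a serious device event would miss expedited notice, because the source rates are not for serious events. The change should be made because safety of the delivery system is the pilot's question and the remedy is small; the descriptive analysis is not invalid without it.

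**What to change.** 1. In 11.1.6 and on the SAE form (electronic and back-up), record relatedness to the study drug and, separately, to the device (pump, needle, adhesive or delivery failure).
2. Define *investigational product* to include the pump.
3. In 11.1.2 and 11.2, extend the definition and the trigger to cover study drug or device.
4. In 11.1.7 and 11.2, name the reference safety document against which device expectedness is judged.
5. In 12.2, add a descriptive listing of AEs by each attribution.
6. Put the same device-relatedness item on the eCRF module for the 11.5 anticipated events, so that worsening HF after failed delivery can be attributed.

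The cost is one or two extra eCRF fields, short wording changes and possibly a few more expedited reports. No visits, subjects or procedures are added. If the eCRF or the brochure already covers the device, the remaining work is to bring the protocol text into line.
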